**Figure 2: Overview of Staggered Design and Independent Data Monitoring Committee (IDMC) Safety Evaluations**

\* Safety evaluation on all available safety data from the entire study, which will include the safety data up to 7 days after vaccination at Day 0 from at least 50 subjects (25 subjects/ group) in the respective age stratum.

For the unblinded IDMC analyses the Quintiles Biostatistics blinded team will produce all the required programs and blinded outputs. These programs and outputs will be transferred to the Quintiles Biostatistics unblinded team. The Quintiles Biostatistics unblinded team will reproduce all outputs based on the actual randomisation schedule and will then be responsible for providing the unblinded outputs to the IDMC members as specified in the latest version of the Biostatistics Blinded to Unblinded Team Handover Document (CS\_TP\_BS0214) for the EBO-Z CHAD3-004 study. Refer to the latest version of the unblinding plan for additional details with regard to the handling of unblinded information.

A separate set of IDMC TLF shells (latest version of EBO-Z\_CHAD3\_IDMC\_Shells) has been created specifically for the IDMC analyses. In addition, the IDMC charter can be referenced for additional information regarding the IDMC analyses.

## 4.2. INTERIM ANALYSIS

An unblinded interim analysis will be conducted when safety and immunology data up to Day 30 have been collected for all subjects. All available safety and immunogenicity data in the interim analysis transfer will be included in the interim analysis. As per protocol, the blinded team will be unblinded at the time of the interim analysis and will produce the unblinded interim analysis TLFs.

The cleaning of the 30-day safety data for each subject will be scheduled to be completed prior to the unblinding in order to keep the blind during data cleaning activities.

The interim analysis is planned once the following has been completed:

- GSK's authorization of the following:
  - o SAP.
  - o Relevant TLF shells.
  - o Analysis cohort assignments.

Document: CHAD3-004-EBO-Z\_Interim\_Final\_SAP\_v1\_0  
Author: Version PPD Number: 1.0 Version Date: 18APR2016

Template No: CS\_TP\_BS016 – Revision 3  
Effective Date: 01May2012

Reference: CS\_WI\_BS005

- Immunogenicity data availability:
  - o At least the Day 30 anti-GP EBOV data should be available.
- Interim analysis data transfer from Data Management.

The interim analysis data transfer should comply with:

- All the data up to Day 30 is clean:
  - o All outstanding data issues and queries resolved. o All unresolvable data issues documented in the Data Handling Report (DHR), a separate document produced by Data Management.
  - o All coding, for example AEs, is completed. o All reconciliation of vendor data with eSource data completed successfully.
- Any additional data post-Day 30 should be as clean as possible.

### 4.3. FINAL ANALYSIS

All final, planned analyses identified in this SAP and relevant set of TLF shells will be performed by the Quintiles Biostatistics blinded team. The final analysis is planned for when all subjects had completed study participation, following:

- GSK's authorization of the following:
  - o Final version of the SAP.
  - o Relevant set of TLF shells. o Analysis cohort assignments.
- Final database lock.
- All immunology data are available.

The final analysis will be performed on a clean database transfer:

- All outstanding data issues and queries were resolved.
- All unresolvable data issues documented in the DHR, a separate document produced by Data Management.
- All coding, for example AEs, is completed.
- All reconciliation of vendor data with eSource data completed successfully.

Document: CHAD3-004-EBO-Z\_Interim\_Final\_SAP\_v1\_0  
Author: Version PPD Number: 1.0 Version Date: 18APR2016

Template No: CS\_TP\_BS016 – Revision 3  
Effective Date: 01May2012

Reference: CS\_WI\_BS005

## 5. ANALYSIS COHORTS

GSK's authorization of the analysis cohort assignments is required at two time points:

- Prior to the interim analysis: Interim analysis cohort authorization.
- Prior to the final analysis: Final analysis cohort authorization:
  - o Prior to the final analysis there will only be a review of the interim analysis cohort assignments as a confirmation of the inclusion of all subjects in the relevant analysis cohorts.

Refer to the relevant analysis cohort assignment documentation (latest version of CHAD3-004-EBO-Z\_Cohort\_Assignment\_Plan) for additional information.

### 5.1. TOTAL ENROLLED COHORT

The Total Enrolled Cohort is defined as all subjects who signed informed consent, regardless of being randomised to either:

- EBO-Z/MENACWY-TT.
- MENACWY-TT/EBO-Z.

The Total Enrolled Cohort will be programmatically derived based on the informed consent information recorded on the Screening form in eSource.

### 5.2. TOTAL RANDOMISED COHORT

The Total Randomised Cohort is defined as all subjects who were randomised to either EBO-Z/MENACWY-TT or MENACWY-TT/EBO-Z, regardless of whether they received a vaccination.

A subject will be programmatically included in the Total Randomised Cohort if the subject had been randomised based on the treatment allocation information recorded on the Visit Day 0 form in eSource or reported in the Interactive Web Randomisation System (IWRS).

For analyses and presentations based on the Total Randomised Cohort, subjects are to be analysed according to the treatment allocated regardless of the treatment received.

### 5.3. TOTAL VACCINATED COHORT (TVC)

The Total Vaccinated Cohort (TVC) is defined as all subjects included in the Total Randomised Cohort who received at least one vaccination. The TVC is defined separately for safety and immunogenicity analyses as described below:

---

Document: CHAD3-004-EBO-Z\_Interim\_Final\_SAP\_v1\_0  
Author: Version PPD Number: 1.0 Version Date: 18APR2016

Template No: CS\_TP\_BS016 – Revision 3  
Effective Date: 01May2012

Reference: CS\_WI\_BS005

- Safety Analysis:
  - o A subject is to be programmatically included in the TVC if the subject has at least one date of vaccination available in the database.
  - o Labelled as 'Total Vaccinated Cohort' in relevant TLF shells.
- Immunogenicity Analysis:
  - o Immunogenicity analysis based on the TVC will include all vaccinated subjects for whom immunogenicity results are available, however, due to the fact that only subjects with data available are to be included per time point for the immunogenicity analysis, there will be no additional elimination required. The TVC for safety and immunogenicity analyses are defined as the same cohort of subjects.

Subjects who received a different treatment to that allocated are to be analysed as described below:

- Analyse subject according to the treatment received at Day 0 (first vaccination).

## 5.4. ACCORDING-TO-PROTOCOL COHORT (ATP)

The According-to-protocol (ATP) Cohort is defined as all evaluable subjects satisfying the following:

- Meet all eligibility criteria.
- Received at least one dose of study vaccine according to protocol procedures and randomisation.
- Randomisation code has not been broken for vaccination at Day 0.
- Comply with the procedures and intervals defined in the protocol.
- Did not receive a concomitant medication/product/vaccination leading to elimination from an ATP analysis (refer to relevant section in the protocol, Section 6.7.2).
- Did not present with a medical condition leading to elimination from an ATP analysis (refer to the relevant section in the protocol, Section 6.8).
- Data concerning immunogenicity endpoint measurements are available.

The ATP Cohort will be used for immunogenicity analyses and will be defined prior to:

- Planned Interim Analysis based on the elimination code process.

Subjects included in the ATP Cohort did not receive a different treatment to that allocated, therefore the analysis would be the same for subjects whether based on the randomised or allocated treatment.

## 5.5. SUB-COHORTS AND SUBSETS OF SUBJECTS

### 5.5.1. SUB-COHORT FOR CELL-MEDIATED IMMUNITY (CMI)

The first approximately 30 subjects randomised per age stratum and group, (180 subjects in total, 90 per group)

will be included in this sub-cohort. Subjects will be included from selected centres (refer to Section 7.2: Multicentre Studies) only. A blood sample for assessment of CMI should be taken from the subjects at the following visits:

- Day 0.
- Day 30.
- Month 6.
- Month 6 + 30 days.
- Month 12.

This sub-cohort will be programmatically assigned based on the relevant treatment allocation information recorded on the Visit Day 0 form in eSource. This sub-cohort will be labelled as the CMI Sub-cohort in the relevant presentations.

### 5.5.2. SUBSET FOR ADDITIONAL TESTING

A subset of the subjects will have additional humoral immunogenicity assays performed. These will be the same subjects as the subjects in the sub-cohort for CMI. These subjects will have the neutralizing antibodies assays performed. Other subjects will have the same samples available, however these samples will be used for other testing and not analysed within this protocol. This subset will be labelled as the Subset for Additional Testing in the relevant presentations.

## 6. GENERAL CONSIDERATIONS

### 6.1. REFERENCE START DATE AND RELATIVE DAY

Reference start date is defined as the date of first vaccination, and equals the Day 0 date. Relative day is calculated relative to the reference start date and is to be used to show start and stop day of an assessment or event. Relative day is calculated as follows:

- $\text{Relative day} = (\text{date of assessment/event} - \text{reference start date}).$

---

Document: CHAD3-004-EBO-Z\_Interim\_Final\_SAP\_v1\_0  
Author: Version PPD Number: 1.0 Version Date: 18APR2016

Template No: CS\_TP\_BS016 – Revision 3  
Effective Date: 01May2012

Reference: CS\_WI\_BS005

Unless otherwise specified, if the date of the assessment/event is partial or missing, relative day and any corresponding durations will not be calculated and will be presented as missing in the listings. Imputed AE dates will be used in order to assign the AEs as either within or outside the relevant collection period and will not be used to calculate an imputed relative day (refer to APPENDIX 2: Partial Date Conventions).

Some presentations might include the relative day relative to the most recent vaccination (refer to Section 6.7.2: Most Recent Vaccination) and will be calculated as follows:

- If the date of the assessment/event is on or after the most recent vaccination:
  - o Relative day to most recent vaccination = (date of event – date of most recent vaccination).

## 6.2. BASELINE

Unless otherwise specified, Baseline is defined as the last non-missing assessment (scheduled or unscheduled) prior to the first vaccination. In the case where the last non-missing assessment and the reference start date coincide, that assessment will be considered pre-baseline (unless specified as post-vaccination). However, adverse events (AEs) starting on the reference start date will be considered post-baseline.

## 6.3. DERIVED TIME POINTS

### 6.3.1. CHAD3-EBO-Z POST-VACCINATION TIME POINTS

As a first step, safety and/or immunogenicity results will be presented by treatment administered at Day 0.

In a second step, all available data post-vaccination with the investigational vaccine (Day 0 for the EBOZ/MENACWY-TT and Month 6 for the MENACWY-TT/EBO-Z treatment groups, respectively) will be pooled. All available safety and immunogenicity data following the ChAd3-EBO-Z vaccination in both the treatment groups will be pooled at the time points as specified in Table 2: Derivation of ChAd3-EBO-Z Post-vaccination Time Points:

**Table 2: Derivation of ChAd3-EBO-Z Post-vaccination Time Points**

ChAd3-EBO-Z Post-vaccination Time Point	Treatment Group	Visit
0 Days Post-vaccination with EBO-Z	EBO-Z/MENACWY-TT	Day 0
	MENACWY-TT/EBO-Z	Month 6
6 Days Post-vaccination with EBO-Z	EBO-Z/MENACWY-TT	Day 6

Document: CHAD3-004-EBO-Z\_Interim\_Final\_SAP\_v1\_0  
 Author: Version PPD Number: 1.0 Version Date: 18APR2016

Template No: CS\_TP\_BS016 – Revision 3  
 Effective Date: 01May2012

Reference: CS\_WI\_BS005

	MENACWY-TT/EBO-Z	Month 6 + 6 Days
30 Days Post-vaccination with EBO-Z	EBO-Z/MENACWY-TT	Day 30
	MENACWY-TT/EBO-Z	Month 6 + 30 Days
3 Months Post-vaccination with EBO-Z	EBO-Z/MENACWY-TT	Month 3
	MENACWY-TT/EBO-Z	Month 9
6 Months Post-vaccination with EBO-Z	EBO-Z/MENACWY-TT	Month 6
	MENACWY-TT/EBO-Z	Month 12

## 6.4. RETESTS, UNSCHEDULED VISITS AND EARLY TERMINATION DATA

In general, for by-visit summaries, data recorded at the scheduled visit will be presented. Unscheduled assessments will not be included in by-visit summaries, but may contribute to the Baseline value.

In the case of a retest (same visit number assigned), the latest available test result as provided in the data transfer for that visit/time point will be used for by-visit summaries.

Listings will include scheduled and unscheduled assessments.

## 6.5. WINDOWING CONVENTIONS

No visit windowing will be performed for this study.

## 6.6. STATISTICAL TESTS

Unless otherwise specified, the default summary statistics will be the following:

- Quantitative variables:
  - o Number of subjects in each category (n).
  - o Mean.
  - o Standard deviation (SD).
  - o Median.
  - o Minimum.
  - o Maximum.
  - o First quartile (Q1).
  - o Third quartile (Q3).

Document: CHAD3-004-EB0-Z\_Interim\_Final\_SAP\_v1\_0  
 Author: Version PPD Number: 1.0 Version Date: 18APR2016

Template No: CS\_TP\_BS016 – Revision 3  
 Effective Date: 01May2012

Reference: CS\_WI\_BS005

- In case of log-transformed data for quantitative variables, the default summary statistics are to be as follows:
  - o Number of subjects in each category (n).
  - o Geometric mean. o Geometric SD.
  - o Median. o Minimum. o Maximum. o Q1. o Q3.
- Qualitative variables:
  - o Number of subjects in each category (n).
  - o The percentage of subjects in each category (%) can be presented relative to either one of the following:
    - The total number of subjects in the relevant analysis cohort (and sub-cohort).
    - The total number of subjects in the relevant analysis cohort (and sub-cohort), with assessments available (observed cases).
    - Total number of subjects in the relevant analysis cohort with returned diary cards.
  - o In the event of missing assessments, a 'Missing' category showing the number of subjects with missing assessments will be presented. Percentage of subjects with missing data will not be presented.

## 6.7. COMMON CALCULATIONS

### 6.7.1. CHANGE FROM BASELINE

For quantitative measurements, change from Baseline will be calculated as:

- Change from Baseline at Day x = (Result at Day x – Baseline Result).

If a result/value is missing, the change from Baseline will be presented as missing in the listing; hence no imputation for a missing change from Baseline will be performed.

### 6.7.2. MOST RECENT VACCINATION

Most recent vaccination prior to assessment/event:

- Calculate the difference in the assessment/start date and all available vaccination dates.

---

Document: CHAD3-004-EBO-Z\_Interim\_Final\_SAP\_v1\_0  
Author: Version PPD Number: 1.0 Version Date: 18APR2016

Template No: CS\_TP\_BS016 – Revision 3  
Effective Date: 01May2012

Reference: CS\_WI\_BS005

- o Assessments: Days since vaccination (Day 0/Month 6) = (Assessment date – vaccination date [Day 0/Month 6]).
- o Events: Days since vaccination (Day 0/Month 6) = (Event start date – vaccination date [Day 0/Month 6]).
- For previous calculation (difference in assess/start date and available vaccination dates), only consider those vaccinations where the days since vaccination is  $\geq 0$  and determine the vaccination (Day 0/Month 6) for which the days since vaccination (as calculated in the previous step) is a minimum.
- Assign the vaccination selected in the previous step (minimum days since vaccination determination) as the most recent.

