### 9.1.4. Clinical laboratory parameters and other abnormal assessments qualifying as adverse events or serious adverse events

In absence of diagnosis, abnormal laboratory findings (*e.g.*, clinical chemistry, haematology) or other abnormal assessments (*e.g.*, vital signs measurements) that are judged by the Investigator to be clinically significant will be recorded as AE or SAE if they meet the definition of an AE or SAE (refer to [Sections 9.1.1](#) and [9.1.2](#)). Clinically significant abnormal laboratory findings or other abnormal assessments that are present at baseline and significantly worsen following the start of the study will also be reported as AEs or SAEs.

The Investigator will exercise his or her medical and scientific judgement in deciding whether an abnormal laboratory finding or other abnormal assessment is clinically significant.

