## 13. STUDY VACCINATION

The following listing is planned for presentation for Total Randomised Cohort:

- Vaccination administration.

---

Document: CHAD3-004-EBO-Z\_Interim\_Final\_SAP\_v1\_0  
Author: Version PPD Number: 1.0 Version Date: 18APR2016

Template No: CS\_TP\_BS016 – Revision 3  
Effective Date: 01May2012

Reference: CS\_WI\_BS005

The following table is planned for presentation for the Total Randomised Cohort:

- Vaccination administration:
  - o Number and percentage of subjects with a vaccination administration at each relevant visit.
  - o Percentage will be calculated relative to the total number of subjects in the relevant analysis cohort.

The following vaccination variables, as presented in the planned TLF shells, will be collected on the Treatment Allocation and Vaccination form in eSource:

- Vaccination administered:
  - o Yes.
  - o No.
- Vaccination site:
  - o Deltoid.
  - o Thigh.
  - o Other, specify.
- Vaccination side:
  - o Right.
  - o Left.
- Vaccination route:
  - o Intramuscular.
  - o Other, specify.
- Date and time of vaccination.

Document: CHAD3-004-EBO-Z\_Interim\_Final\_SAP\_v1\_0  
Author: Version PPD Number: 1.0 Version Date: 18APR2016

Template No: CS\_TP\_BS016 – Revision 3  
Effective Date: 01May2012

Reference: CS\_WI\_BS005

- Comment on vaccination administration.

- Reason for non-administration:

- o Serious  
Adverse Event  
related to  
study  
participation  
or to a GSK  
concurrent  
medication. o  
Serious  
Adverse Event  
not related to  
study  
participation  
or to a GSK  
concurrent  
medication. o  
Non-  
Serious  
Adverse Event.  
o Other,  
specify.

- Decision maker for non-administration:

- o Investigator. o  
Subject. o  
Legally  
acceptable  
representative.

The following contraindication variables, as presented in the planned TLF shells, will be recorded on the Contraindication Review form in eSource:

- Fever (temperature  $\geq 37.5^{\circ}\text{C}$ ):
  - o Yes. o  
No.
- Clinically significant immunosuppressive or immunodeficient condition:
  - o Yes. o  
No.
- Pregnant: o Yes. o No.

Document: CHAD3-004-EBO-Z\_Interim\_Final\_SAP\_v1\_0  
Author: Version PPD Number: 1.0 Version Date: 18APR2016

Template No: CS\_TP\_BS016 – Revision 3  
Effective Date: 01May2012

Reference: CS\_WI\_BS005

- Had anaphylaxis following vaccine administration:
  - o Yes.
  - o No.

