All unsolicited AE incidence tables will be repeated for the following pooling of AEs, presented per age stratum:

- AEs following the active ChAd3-EBO-Z vaccination; hence:
  - o EBO-Z/MENACWY-TT subjects: Unsolicited AEs within the reporting window following Day 0 vaccination.
  - o MENACWY-TT/EBO-Z subjects: Unsolicited AEs within the reporting window following Month 6 vaccination.

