Author: PPD Version Number: 2.0 Version Date: 14JUN2017

Template No: CS\_TP\_BS016 – Revision 3

Reference: CS\_WI\_BS005

Effective Date: 01May2012

Copyright © 2012 Quintiles Transnational Corp. All rights reserved.

The contents of this document are confidential and proprietary to Quintiles Transnational Corp. Unauthorised use, disclosure or reproduction is strictly prohibited.

- Results following the active ChAd3-EBO-Z vaccination; hence:
  - o EBO-Z/MENACWY-TT subjects: Laboratory results following Day 0 vaccination.
  - o MENACWY-TT/EBO-Z subjects: Laboratory results following Month 6 vaccination.

The following figure is planned for presentation based on the Total Vaccinated Cohort:

- Platelet: Quartile Distribution following Day 0 Vaccination:
  - o Box and whisker plot presenting the platelet distribution up to Day 30. o The mean, median as well as the Q1 and 3 values will be presented on the figure. o The treatment groups will be presented separately on the same figure.

The following laboratory variables, as presented in the planned TLF shells, will be recorded on the Blood Sampling form in eSource:

- Date and time of sample collection:
  - o Haematology samples.
  - o Biochemistry samples.

The following laboratory variables, as presented in the planned TLF shells, will be recorded on the Laboratory Results form in eSource:

- Date of sample collection:
  - o Haematology samples.
  - o Biochemistry samples.
- Result and unit.
- Significance:
  - o Not clinically significant (NCS).
  - o Clinically significant (CS).

The following laboratory variables, as presented in the planned TLF shells, will be recorded on the Malaria RDT and Results form in eSource:

- Date and time of assessment.
- Result:
  - o Positive.
  - o Negative.
- Malaria treatment prescribed per local/national requirements:
  - o Yes.
  - o No.
- Prescribed malaria treatment completed:

---

Document: CHAD3-004-EBO-Z\_Interim\_Final\_SAP\_v2\_0

Author: PPD Version Number: 2.0 Version Date: 14JUN2017

Template No: CS\_TP\_BS016 – Revision 3

Reference: CS\_WI\_BS005

Effective Date: 01May2012

- - o Yes.
  - o No.

The following laboratory variables, as presented in the planned TLF shells, will be recorded on the Pregnancy Test form in eSource:

- Date and time of assessment.
- Result:
  - o Positive.
  - o Negative.

The following pregnancy variables, as presented in the planned TLF shells, will be recorded on the Pregnancy Report form in eSource:

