#### 15.4.1. DERIVATIONS

Based on the aforementioned variables, the following variables will be derived:

- Relative day:
  - o Calculated relative to Day 0 vaccination (refer to Section 6.1: Reference Start Date and Relative Day).
- Change from Baseline for results in System of International (SI) units (refer to Section 6.7.1: Change from Baseline).
- Derived decrease categories (%):
  - o  $\text{Change from Baseline} / \text{value at Baseline} \times 100$
- Toxicity grade for selected laboratory tests (refer to APPENDIX 6: Laboratory Toxicity Grading for derivation details).
  - o Maximum grade overall will also be derived as the highest post-vaccination toxicity grade across all post-baseline visits and time points.
- Reference range indicator based on the results in SI units.
  - o Low: Result < reference range lower limit.
  - o Normal: Result  $\geq$  reference range lower limit AND result  $\leq$  reference range upper limit. o High: Result > reference range upper limit.

For clinical laboratory results below or above the limit of quantification will be handled as follows:

- Assign as equal to the limit of quantification, for example '<x' will be assigned as x for analysis purposes. SI conversions can be applied to the derived result. In the listings the result will be presented as the SI value (after conversion) with the qualifier symbol concatenated, for example '<y' in SI unit.

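### In the pooled post-ChAd3-EBO-Z safety tables, control-group findings made at Month 6 before the dose can be counted as post-vaccine findings

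*SAP*

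**What the plan says.** **Events.** SAP 6.7.2 first tells the programmer to "Calculate the difference in the assessment/start date and all available vaccination dates". It then says to "only consider those vaccinations where the days since vaccination is" zero or more, and to take the smallest difference. Clock time plays no part. SAP 15.1.1 uses this derivation for unsolicited AEs and defines dose at onset as the most recent dose before the AE began. The pooled tables in 15.1.2 then take, for the control group, "MENACWY-TT/EBO-Z subjects: Unsolicited AEs within the reporting window following Month 6 vaccination". The protocol's 30-day window (11.1) includes the day of vaccination.

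**Laboratory.** SAP 15.4 pools, for the control group, "MENACWY-TT/EBO-Z subjects: Laboratory results following Month 6 vaccination". It does not cite 6.7.2. Pooled time points are assigned by visit in Table 2 (SAP 6.3.1), where the control group's Month 6 visit is the zero-day post-ChAd3-EBO-Z time point. SAP 15.4.1 derives an overall maximum grade as the "highest post-vaccination toxicity grade across all post-baseline visits and time points".

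**Baseline.** SAP 6.2 fixes baseline before the first vaccination. Of an assessment on that date it says "that assessment will be considered pre-baseline (unless specified as post-vaccination"). AEs starting on that date count as post-baseline. There is no matching rule for assessments on the date of the Month 6 dose.

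**Times.** SAP 13 collects "Date and time of vaccination". SAP 15.1 collects AE start date and time, and 15.4 collects date and time of blood sampling.

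**The concern.** The pooled tables are meant to describe safety after ChAd3-EBO-Z in all 600 children. Half of those doses are given at Month 6, at a visit where haematology and biochemistry blood is also drawn (Protocol Table 5). If that blood is taken before the injection, an abnormality in it cannot be an effect of ChAd3-EBO-Z. An AE with a recorded start time earlier than the injection cannot be one either.

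Laboratory abnormalities and 30-day unsolicited AEs are both primary endpoints. Protocol 11.8 states that the pooled data cannot be presented against control, so a comparator will not show up a misattributed finding. The laboratory route is also one-sided: no haematology or biochemistry draw is scheduled at the Day 0 visit, and a Screening sample taken on the same day falls under the pre-baseline rule in 6.2.

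**Working it through.** No figure in the plan depends on this rule, so there is none to reproduce. The check applies the rules as written.

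**1. Events under 6.7.2.** Take an illustrative control child with Nimenrix at Day 0 and ChAd3-EBO-Z 182 days later at 10:30.

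| Recorded start | Days since Nimenrix | Days since ChAd3-EBO-Z | 6.7.2 assigns to | Date and time would assign to |
|---|---|---|---|---|
| Month 6 day, 09:00 | 182 | 0 | ChAd3-EBO-Z | Nimenrix |
| Month 6 day, 15:00 | 182 | 0 | ChAd3-EBO-Z | ChAd3-EBO-Z |
| Day before | 181 | negative, not eligible | Nimenrix | Nimenrix |

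The first row contradicts the definition of dose at onset in 15.1.1. Assigned to Nimenrix, that event would lie about 182 days after the dose, outside the 30-day window. It would be listed but not counted.

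**2. How a laboratory finding becomes an AE.** Under Protocol 9.1.4, an abnormal result "judged by the Investigator to be clinically significant will be recorded as AE or SAE" if it meets the definition of either. One found in the Month 6 sample and given that day's date falls into row one.

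**3. Laboratory tables.** Three provisions combine:
- Table 2 calls the control group's Month 6 visit zero days post-vaccination.
- Baseline precedes the first vaccination, so Month 6 is a post-baseline visit.
- The maximum grade runs over all post-baseline visits and does not leave Month 6 out.

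Contrast the pooled CMI overall response (SAP 14.2.1.1), which for the control group uses only Month 6 + 30 days and Month 12.

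**4. Is the Month 6 blood drawn before the dose?** No sentence says so. The inference rests on Protocol 11.2, which pairs Month 6 with Month 6 + 30 days in the control group, and on SAP 14.1.1, where response needs a pre- and a post-vaccination value. SAP 14 repeats the immunogenicity tables on Table 2 time points, where control-group Month 6 parallels Day 0 in the other group. Safety blood is drawn at the same visit.

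**5. Size.** The documents give no rate, so p, the share of about 300 control children with a pre-dose Month 6 finding, is assumed. Upper bound: children added = 300p; percentage points = 100 × 300p / 600.

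| p | Children added, at most | Points of 600, at most |
|---|---|---|
| 1% | 3 | 0.5 |
| 5% | 15 | 2.5 |
| 10% | 30 | 5.0 |

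The points are the same within an age stratum (100p of 200). The bound is reached only if no such child has another counted finding. For the maximum grade, suppose each panel carries probability p independently and three later panels follow (Month 6 + 6 days, Month 6 + 30 days, Month 12). Children added are then 300 × p × (1 − p)³:
- 1%: 300 × 0.01 × 0.970 = 2.9
- 5%: 300 × 0.05 × 0.857 = 12.9
- 10%: 300 × 0.10 × 0.729 = 21.9

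Positive correlation between a child's panels lowers these further, to zero if the panels always agree.

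**The case against.** Much of the case against stands.

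- A reader might infer that 6.7.2 itself moves the Month 6 blood results. It does not. SAP 15.4 never cites it, laboratory relative day runs from Day 0, and pooling is by visit. Rewriting 6.7.2 alone would not change one laboratory value.
- On its plain wording, the pooling rule in 15.4 takes results that follow the Month 6 dose, which would exclude a pre-dose sample. In by-visit tables Month 6 is a separate row. The table shells, which could settle the maximum grade, are not available. But Table 2 says otherwise, and no text excludes the panel.
- Counting same-day AEs as post-vaccination is deliberate: 6.2 does so at the first dose and the protocol window includes the day of vaccination. It is also the conservative choice for safety. That supports the rule when the order is unknown, but not when a recorded time shows that the event came first.
- The AE route is narrow. Only clinically significant results become AEs, Protocol 9.1.1 excludes conditions present before study vaccination, and 9.3.1 requires only AEs starting in the 30 days after a dose. A pre-dose finding enters only if a site records it as an AE with that date. However, medical history is scheduled only at Screening and Day 0, so at Month 6 there is no scheduled alternative place for it.
- AE listings are to show days relative to the most recent vaccination, so day-zero onsets can be identified by hand.

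**Conclusion.** The point holds for the pooled post-ChAd3-EBO-Z safety tables. As written, an AE that began before the Month 6 dose on the same day is attributed to ChAd3-EBO-Z, and the control group's Month 6 panel is not excluded from the maximum post-vaccination grade. The laboratory part rests on the inference that the blood precedes the dose.

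A reader might conclude that two primary endpoints are biased upwards by a known amount. The documents do not support that. The first-step comparison by Day 0 treatment is untouched, as are the by-visit rows and the pooled CMI overall response, and all analyses are descriptive. The size is unknown: at assumed rates of 1% to 10%, the addition is at most 3 to 30 children, 0.5 to 5 points of 600, and smaller where children have other counted events or correlated panels. It is worth correcting because the pooled tables have no control arm and the data needed are already collected.

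**What to change.** 1. **SAP 6.7.2:** for events dated on a vaccination day, compare recorded start time with recorded vaccination time and assign events that began earlier to the previous vaccination. Keep the current date rule when either time is missing.
2. **SAP Table 2:** relabel the control group's Month 6 visit as the pre-dose reference for ChAd3-EBO-Z.
3. **SAP 15.4 and 15.4.1:** exclude that panel from the pooled post-ChAd3-EBO-Z maximum grade and out-of-range counts.

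The cost is a few lines of text and minor programming, with no new data. The drawback is that a same-day AE with an inaccurate recorded time could be assigned to the wrong dose.
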